	
To test for heterogeneity across strata, the exact test of Zelen will be performed testing whether the treatment effect differs between the 2 strata included in the primary analysis.
 
Progression-free survival will be analyzed using a stratified log-rank test using the Breslow method to handle ties (Breslow, 1974). The analysis will be stratified by primary tumor location (GB/Non-GB).
 
Overall survival will be analyzed using the methods outlined above for PFS. For Part 1, OS will be analyzed twice. A preliminary analysis of OS will be performed at the time of the primary analysis of ORR and PFS. It is anticipated that the OS data at this time will be immature, thus a second analysis of OS is planned for when approximately 95 patients (approx. 79%) have an OS event. The second analysis of OS will be considered the primary analysis of OS for Part 1 of the trial. For Part 2, the primary analysis of OS will be performed when 247 patients have experienced an OS event. Further details will be provided in the study SAP.
 
Duration of response will be listed and summarized descriptively for the duration of response in responding patients, including the associated Kaplan-Meier curves.
 
Disease control rate will be analyzed using the methods described above for ORR.
 
Tumor size is a secondary endpoint in Part 1 and will be used to assess the exploratory objective of evaluating the role of HER family expression levels as predictors of benefit to varlitinib. Tumor size will be analyzed by analysis of covariance (ANCOVA).
 
Plasma sampling will be conducted for population PK evaluation in Parts 1 and 2 of the study and will use an NLME. PK sampling of all patients is planned for Part 1 of the study while sparse PK sampling is planned for Part 2. For the sparse PK sampling in Part 2, the double-blind design will be maintained and blood samples will be collected from a selected number of patients without limiting the sampling to varlitinib patients only.
 
All PK data will be analyzed according to treatment received. Deviations that have the potential to significantly affect the PK will be reviewed. The population, and decisions regarding which profiles are usable, will be defined by the Study Team Physician, Pharmacokineticist, and Statistician prior to unblinding or any analyses being performed.
 
ECG/QT Analysis (Safety Lead-in and Part 1)
 
General Principles
 
Baseline will be defined as the mean of the triplicate ECG readings performed pre-dose on Day 1. On Day 1, pre-dose is defined as 2 sets of triplicate ECGs taken 45 minutes and 5 minutes prior to dosing. The ECG values from these 2 sets of ECGs will be averaged to create the baseline value. Similarly, for all other time points, for each ECG parameter, each patient's mean will be calculated from the triplicate readings and the mean value will be used.
 
The final ECG assessments (including interval measurements) will be made by the Core ECG laboratory. The Part 1 electrocardiographic Core ECG Laboratory assessments constitute the study's primary assessment of ECG/QTc. Any analysis of ECG data from the Safety lead-in is considered exploratory.
 
Due to the non-randomized, open label design of the Safety lead-in, data from the Safety lead-in will be presented separately from data from Part 1 of the study. Furthermore, ECG/QT outputs will be made available to the DSMB for consideration when determining whether the study should progress to Part 1.

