7.1.3.2 Pharmacokinetic Sampling

Safety Lead-in

Blood samples for PK analysis of varlitinib (and any relevant circulating metabolites), capecitabine, and 5-FU (active capecitabine metabolite) will be collected at the following time points in the Safety lead-in part only:

- Cycle 1 Day 1: 5 minutes pre-dose, 0.5, 1, 2, 3, 4, 5, 6, 8.5, 10, and 12 hours post-dose
- Cycle 1 Day 8: 20 minutes pre-dose, 0.5, 1, 2, 3, 4, 5, 6, 8.5, 10, and 12 hours post-dose

- Cycle 1 Day 14: 5 minutes pre-dose, 0.5, 1, 2, 3, 4, 5, 6, 8.5, 10, and 12 hours post-dose

Patients must withhold taking the morning dose of varlitinib and capecitabine until pre-dose PK sample is collected. The actual sample date and time of all PK samples must be recorded in the CRF.

In addition, unscheduled PK collected 7 days following dose reduction of varlitinib at any cycle of treatment: up to 5 minutes pre-dose, 0.5, 1, 2, 3, 4, 5, 6, 8.5, 10, and 12 hours post-dose if required.

Part 1 and Part 2

In Part 1 and Part 2, PK samples will be obtained for the PK evaluation of varlitinib (and any relevant circulating metabolites). PK samples will be collected at the following time points:

Part 1 (All patients)

- Cycle 1 Day 1: 5 minutes pre-dose, 1.5, 3, 5, and 8 hours post-dose
- Cycle 1 Day 8: 20 minutes pre-dose, 1.5, 3, 5, and 8 hours post-dose
- End of study after full drug washout: 28 days after last dose at the patient's safety follow-up visit

Part 2 (Sparse Sampling)

- Cycle 1 Day 1: 5 minutes pre-dose, 1-3 hours post-dose, 3-5 hours post-dose, and 5-8 hours post-dose
- Cycle 2 Day 1: 20 minutes pre-dose, 1-3 hours post-dose, 3-5 hours post-dose, and 5-8 hours post-dose

In order to maintain the double-blind design of the study, blood samples will be collected from all subjects in Part 1 for plasma measurements of varlitinib and its potential relevant circulating metabolites. For the sparse PK sampling in Part 2, the double-blind design will also be maintained and blood samples will be collected for a selected number of subjects, without limiting the sampling to the varlitinib subjects only.

All PK data will be analyzed according to treatment received. Deviations that have the potential to significantly affect the PK will be reviewed. The population, and decisions regarding which profiles are usable, will be defined by the Study Team Physician, Pharmacokineticist, and Statistician prior to any analyses being performed.

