Following Part 1 of the study, a formal statistical analysis will be performed to assess the potential impact of varlitinib and capecitabine on changes in the ECG parameters.

The statistical stepwise approach will be used to separate the cardiodynamic effect of varlitinib from normal circadian fluctuation in the ECG values and from the effect of capecitabine:

1. ANOVA mixed effects comparison of the absolute values of ECG parameters at each time point vs baseline using treatment as a fixed effect in order to evaluate the contribution of circadian fluctuation and

to determine how treatment differences contribute to the changes. The ECG parameter values will be log-transformed and the resulting output will include the geometric mean ratio for test vs reference with the corresponding confidence interval and p-value. Interaction term, time point x treatment, will be also evaluated if the data allow.

2. ANOVA comparison of the absolute values of ECG parameters as well as change from baseline (Δ ECG) between treatments for each post-dose time point assessed separately in order to separate the varlitinib effect from that of capecitabine. The ECG parameter values will be log-transformed and the resulting output will include the geometric mean ratio for test vs reference with the corresponding confidence interval and p-value. Δ ECG will be tested as untransformed and log-transformed parameters to avoid bias from discarding 0 Δ ECG values from the comparisons.
3. Exposure-Response Analysis: Linear mixed effect model between Δ QTcF and time matched concentrations of varlitinib and other potential metabolites if measured and as appropriate. Other ECG variable may be similarly analyzed and other models used, if appropriate.
 - 3.1 Δ QTcF will be calculated as the difference between each time point value and the average baseline value for each arm with the combination varlitinib/capecitabine treatment.
 - 3.2 $\Delta\Delta$ QTcF will be calculated for each patient in the combination arm individually as the difference between the Δ QTcF value for the arm with combination varlitinib/capecitabine treatment and the average value of all patients in the capecitabine alone arm matching time point. Other ECG parameters may also be used in the analysis including QTcB, heart rate, etc to provide supporting information.
 - 3.3 Base linear mixed effect model will include patients as a random effect.

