 - 3.4 The total dose of capecitabine may be included as a fixed effect in the model to account for differences in total doses received by subjects with different body surface area.
4. Linear mixed effect model between Δ QTcF parameters and time matched concentrations of capecitabine and 5-FU (metabolite of capecitabine) and other potential metabolites if measured and as appropriate

- 4.1. $\Delta QTcF$ will be calculated for all patients in both arms as the difference between each time point value and the average baseline value.
- 4.2. Base linear mixed effect model will include patients as a random effect and treatment (capecitabine alone or in combination with varlitinib) as a fixed effect; the total capecitabine dose may also be used as a fixed effect.
5. Different covariates may be included in the complex models in addition to the base model as fixed effects such as time point in order to ensure the model feasibility and to evaluate covariates influential to ECG parameters.

The results of the fitted models will be presented using statistical parameters such as the geometric mean ratios and corresponding confidence intervals (for ANOVA) and estimates of the slope, and associated confidence interval for the linear mixed effect models.

In addition, the following graphic exploration of the exposure-ECG relationship may be performed:

- Residual plots to predict results
- Double Y plots with time on the X axis and time matched values of PK concentrations for varlitinib and capecitabine on the Y1 axis, ΔECG on the Y2 axis to determine the possibility of hysteresis between drug concentration and cardiodynamic effects
- Regression/scatter plots with time matched concentrations of varlitinib and capecitabine on the X axis and ΔECG on the Y axis
- Regression/scatter plots with varlitinib or capecitabine non-compartmental PK parameters of C_{max} , C_{trough} , AUC_{tau} and others on the X axis and maximum ΔECG on the Y axis
- Forest plots for different categories in ECG changes vs mean (SD) non-compartmental PK parameters for varlitinib or capecitabine on the X axis

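### The base concentration–QTcF models do not require a time-point term, so within-day QT drift can bias the slope in step 4, and in step 3 if ΔQTcF is the response

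*Protocol*

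**What the plan says.** Protocol 8.5.2.3 states the aim for Part 1: "The statistical stepwise approach will be used to separate the cardiodynamic effect of varlitinib from normal circadian fluctuation in the ECG values", and also from the effect of capecitabine. Five steps follow, and SAP 7.11.4.2 repeats them in substance.

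- **Steps 1 and 2** compare ECG values with baseline at each time point, and compare the arms at each post-dose time point.
- **Step 3** models varlitinib. Its heading relates ΔQTcF "and time matched concentrations of varlitinib and other potential metabolites if measured and as appropriate". Step 3.2 then defines ΔΔQTcF as the patient's ΔQTcF minus a control mean: "and the average value of all patients in the capecitabine alone arm matching time point". Step 3.3 reads "Base linear mixed effect model will include patients as a random effect". Neither document says which of the two responses enters the model. The protocol's step 3.1 speaks of the combination arm, while the SAP's speaks of each arm.
- **Step 4** models capecitabine and 5-FU. Step 4.2 reads "Base linear mixed effect model will include patients as a random effect and treatment (capecitabine alone or in combination with varlitinib", with treatment as a fixed effect. Total capecitabine dose is optional.
- **Step 5** is where time appears: "Different covariates may be included in the complex models in addition to the base model as fixed effects such as time point".

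Baseline comes from two pre-dose triplicate sets on Day 1: "The ECG values from these 2 sets of ECGs will be averaged to create the baseline value". Part 1 sampling (Protocol 7.1.3.2) is "Cycle 1 Day 1: 5 minutes pre-dose, 1.5, 3, 5, and 8 hours post-dose", with the same post-dose hours on Day 8. The Day 1 and Day 8 doses are supervised morning doses, and capecitabine is taken with food at the same time (Protocol 5.4.8).

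**The concern.** Every patient doses in the morning and is measured at the same hours, so concentration is largely a function of time since dose, and therefore of clock time and meals. ΔQTcF from a pre-dose baseline carries whatever QTcF does over those hours without drug. A model with concentration and no time term must assign any part of that drift that resembles the concentration curve to the drug.

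In step 4 nothing else in the model can absorb it. Both arms take capecitabine, so the treatment term shifts the mean between arms and leaves shared drift in place. In step 3 the same applies if ΔQTcF is the response. If ΔΔQTcF is the response, subtracting the control mean at the same time point removes the shared drift.

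At stake are the reported slope estimates and confidence intervals for QT effect against concentration. Drift in the same direction as the curve can create a slope; drift against it can hide one. The term that guards against this is left to a choice made after the data are seen.

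**Working it through.** **Plan's own figure.** There is none to reproduce. The documents give no test level, variance, drift size or sample-size argument for these models.

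**Inputs from the documents.** 60 patients per arm (Protocol 5.3.1). Day 1 at 1.5, 3, 5 and 8 h; Day 8 pre-dose, 1.5, 3, 5 and 8 h (Protocol 7.1.3.2), giving 4 + 5 = 9 post-baseline records per patient. Base-model terms as in steps 3.3 and 4.2.

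**Assumptions, not in the documents.** Within-patient SD 8 ms (12 ms also tried). Drift amplitude 0 to 10 ms, shaped as a mid-day hump, an early peak near 2 h, or a straight line over 8 h. One-compartment oral profiles: a slower, accumulating varlitinib curve and a fast capecitabine curve. Two-sided 5% Wald test on a random-intercept model.

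**Why the slope is biased.** Suppose the drug has no effect and ΔQTcF = d(t) + patient effect + error. Shared drift d(t) varies only within patients, so the fitted slope has expectation close to

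Σ(c − c̄ᵢ)(d − d̄) / Σ(c − c̄ᵢ)²,

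where c̄ᵢ is patient i's mean concentration. It is proportional to drift size and depends on how closely drift follows the concentration curve.

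**Simulation, true slope zero.** 1,000 trials per row. Monte Carlo standard error near 5% is √(0.05 × 0.95 / 1000) = 0.7 points. Slopes are in ms per mean peak concentration.

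| Drift | Step 3 base, ΔQTcF: rejection (mean slope) | Step 4 base: rejection (mean slope) | Step 3 + time, both arms | Step 4 + time |
|---|---|---|---|---|
| none | 5.2% (0.06) | 4.0% (0.01) | 4.0% | 4.9% |
| hump, 2 ms | 21.2% (1.33) | 6.2% (0.03) | 7.0% | 5.3% |
| hump, 5 ms | 74.0% (3.20) | 4.4% (0.13) | 4.6% | 5.2% |
| early, 2 ms | 16.6% (1.21) | 68.1% (1.47) | 5.0% | 5.3% |
| early, 5 ms | 68.5% (3.04) | 100% (3.69) | 5.9% | 4.2% |
| linear, 2 ms | 5.6% (−0.28) | 28.3% (−0.82) | 4.3% | 4.3% |
| linear, 5 ms | 10.6% (−0.82) | 89.7% (−2.03) | 4.3% | 4.7% |

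The step 4 slopes scale with drift as the formula says. Early peak: 1.47/2 = 0.74 and 3.69/5 = 0.74. Linear: −0.82/2 = −0.41 and −2.03/5 = −0.41. For the hump, 0.13/5 = 0.03, because that shape is nearly uncorrelated with the fast capecitabine curve. Reversing the sign of the drift gave mirror-image slopes. With SD 12 ms and hump drift, step 3 on ΔQTcF rejected 11.2% at 2 ms and 39.8% at 5 ms. Over all scenarios the time factor gave 3.5% to 7.0% in step 3 and 4.1% to 6.1% in step 4.

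**ΔΔQTcF in step 3.** Mean slope was about zero at every drift. Rejection was 9.3% to 13.1%, and 9.7% with no drift at all, so that excess is not due to drift. It arises because the subtracted control mean is treated as known.

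**Step 4 under other assumptions.** With patient SD 10 ms, residual SD 8 ms, concentration CV 50%, absorption 2.0/h and elimination 0.9/h, a hump peaking at 4 h gave 5–6% at 2 ms and 7% at 3 ms. Early-peak and linear shapes gave 39–44% at 2 ms. At 3 ms they gave 68% (early) and 77% (linear) on the four post-dose hours, and 84% and 51% once the Day 8 pre-dose point was added. A further run gave 13–48% at 2 ms and 15–81% at 3 ms, against 3–6% with a time factor. Varying the residual SD from 6 to 12 ms at 3 ms, over two drift shapes, gave 22–94%.

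**The case against.** The case on the other side has real weight.

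- **Time is not absent.** Step 5 names it as a permitted fixed effect. A reader might infer that the plan has no time term at all; it has one, but does not require it.
- **The primary QT analysis is elsewhere.** A reader might infer that the study's main QT conclusion is compromised. The documents give primary status to the time-based Part 1 ECG analysis by the core laboratory (Synopsis, Study Assessments; SAP 3.2), not to a concentration slope. The step 2 comparison of randomised arms at each time point is free of shared drift.
- **The modelling is conditional.** Protocol 8.5.2.3 makes it optional, to follow if varlitinib appears to have a meaningful ECG effect. The rates above describe the model when fitted, not the whole strategy.
- **Step 4 may have no data.** Protocol 7.1.3.1 drops the Part 1 capecitabine and 5-FU assays if the lead-in shows no relevant interaction.
- **The stated aim concerns varlitinib**, and ΔΔQTcF would meet it as far as drift is concerned.
- **No decision rule** is attached to the slope, only an estimate and interval.

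All of this stands and limits the point's weight. It does not remove it. SAP 7.11 says that PK/PD analyses of QTc prolongation will be performed in Parts 1 and 2. The SAP output list includes capecitabine concentration tables for Parts 1 and 2 and capecitabine–QTcF scatter plots. An optional analysis still needs a sound base model when it is run, and an interval centred on a biased slope misleads without any formal test.

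**Conclusion.** The point holds in limited form. As written, the base models can turn within-day drift into a concentration slope: in step 4 whenever it is run, and in step 3 if ΔQTcF is the response, as its heading says. Whether step 3 is affected cannot be settled from the text.

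A reader might infer that a false slope is inevitable. It is not: at 2 to 3 ms of drift, the simulated rates run from near nominal, when drift is nearly uncorrelated with the concentration curve, to above 80%, when it follows the curve closely. With a time factor they return to about 5%. The size rests entirely on assumed drift, SDs, PK profiles and a 5% two-sided level, none of which the documents give. The direction of the argument does not depend on those values, because it follows from the fixed sampling hours, the pre-dose baseline and, for step 4, the lack of a capecitabine-free arm.

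The affected analyses are secondary and conditional, so this is a model-specification point worth correcting, not a threat to the primary ECG analysis.

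**What to change.** In Protocol 8.5.2.3 and SAP 7.11.4.2:

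1. Make nominal time point, by day, a fixed effect in the step 4 base model, and in the step 3 base model when ΔQTcF is the response. Remove it from the optional list in step 5.
2. Name the step 3 response. ΔQTcF in both arms, with control-arm varlitinib concentration set to 0 and time point in the model, is preferable. It handles drift and also avoids the 9% to 13% rejection seen when the subtracted control mean is treated as known.
3. Describe the placebo arm's change from baseline as capecitabine plus circadian plus meal effect, not as the effect of capecitabine alone.

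No new data are needed. The cost is some precision, because the slope is then estimated mainly from differences between patients at the same time point. In one simulated setting, step 3 on the varlitinib arm alone fell from 88% to 71% apparent power. In step 4, power stayed at about 100% with or without the term, but a result at that ceiling says little about the true cost.

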9 QUALITY ASSURANCE AND QUALITY CONTROL

9.1 Audit and Inspection

Study centers and study documentation may be patient to Quality Assurance audit during the course of the study by the sponsor or its nominated representative. In addition, inspections may be conducted by regulatory authorities at their discretion.

9.2 Monitoring

Data for each patient will be recorded on a CRF. Data collection must be completed for each patient who signs an ICF and is administered study drug.

In accordance with GCP and ICH guidelines, the study monitor will carry out source document verification at regular intervals to ensure that the data collected in the CRF are accurate and reliable.

The Investigator must permit the monitor, the IEC/IRB, the sponsor's internal auditors, and representatives from regulatory authorities direct access to all study-related documents and pertinent hospital or medical records for confirmation of data contained within the CRFs.

9.3 Data Management and Coding

The designated CRO will be responsible for activities associated with the data management of this study. This will include setting up a relevant database and data transfer mechanisms, along with appropriate validation of data and resolution of queries. Data generated within this clinical study will be handled according to the relevant standard operating procedures (SOPs) of the data management and biostatistics departments of sponsor or the designated CRO.

Study centers will enter data directly into an EDC system by completing the CRF via a secure internet connection. Data entered into the eCRF must be verifiable against source documents at the study center. Data to be recorded directly on the eCRF will be identified and the eCRF will be considered the source document. Any changes to the data entered into the EDC system will be recorded in the audit trail and will be FDA CFR 21 Part 11 compliant.

Medical coding will use Medical Dictionary for Regulatory Activities (MedDRA) for concomitant diseases and AEs and WHO Drug for medications.

Missing or inconsistent data will be queried in writing to the Investigator for clarification. Subsequent modifications to the database will be documented.

10 RECORDS AND SUPPLIES

10.1 Drug Accountability

On receipt of the study medication (varlitinib, placebo, and capecitabine), the Investigator (or deputy) will conduct an inventory check of the supplies and verify that study drug supplies are received intact and in the correct amounts as in the patient dosing diary, before completing a supplies receipt. The Investigator will retain a copy of this receipt at the study center and return the original receipt to the study monitor. The monitor may check the study supplies at each study center at any time during the study.

It is the responsibility of the study monitor to ensure that the Investigator (or deputy) has correctly documented the amount of the study drug received, dispensed, and returned on the dispensing log that will be provided. A full drug accountability log will be maintained at the study center at all times. The study monitor will arrange collection of unused study drug returned by the patient. The study monitor will also perform an inventory of study drug at the close-out visit to the study center. All discrepancies must be accounted for and documented.

10.2 Financing and Insurance

Financing and insurance of this study will be outlined in a separate agreement between the designated CRO and the sponsor.

11 ETHICS

11.1 Independent Ethics Committee or Institutional Review Board

Before initiation of the study at each study center, the protocol, the ICF, other written material given to the patients, and any other relevant study documentation will be submitted to the appropriate IEC/IRB. Written approval of the study and all relevant study information must be obtained before the study center can be initiated or the study drug is released to the Investigator. Any necessary extensions or renewals of IEC/IRB approval must be obtained for changes to the study such as amendments to the protocol, the ICF or other study documentation. The written approval of the IEC/IRB together with the approved ICF must be filed in the study files.

The Investigator will report promptly to the IEC/IRB any new information that may adversely affect the safety of the patients or the conduct of the study. The Investigator will submit written summaries of the study status to the IEC/IRB as required. On completion of the study, the IEC/IRB will be notified that the study has ended.

